The ACTH dosage chosen falls well within the range routinely employed, with efficacy, for treatment of MS relapses. It is known that this dose is well-tolerated, with an excellent safety profile. We have selected a 6-month treatment interval, which has become the standard phase II trial duration for multiple sclerosis therapeutic agents. This duration should also provide adequate time to study time of onset of effects of ACTH upon fatigue and whether they sustained over at least several months of medication use.

The primary endpoint of this study is a statistically significant reduction of fatigue in subjects who have RMS and fulfill the definition of PMSF when treated with ACTH compared to placebo. Known biological actions, both directly and indirectly, of ACTH upon the CNS make it a plausible candidate agent for the reduction of PMSF.

The secondary endpoints are: 1) statistically significant improvement in patient self-assessment of quality of life; 2) statistically significant reduction in patient self-assessment of depression; 3) statistically significant reduction in patient self-assessment of sleepiness measures when treated with ACTH, as compared to placebo, and 4) the safety and tolerability of twice weekly ACTH injections compared to placebo. The rationales for the secondary endpoints are: 1) the demonstration that quality of life improvements with ACTH use in patients with PMSF would increase the clinical significance or ACTH-induced reduction in PMSF; 2) fatigue and depression are so strongly correlated in patients with MS that reduction in depression with ACTH treatment would strengthen the possibility that depression and fatigue share, at least in part, a common mechanism, and a parallel decrease in depression would strengthen the validity of the potential causative action of ACTH upon fatigue; 3) sleepiness is strongly correlated with MS-induced fatigue and thus reduction in daytime sleepiness would be an additional measure of validity for ACTH-induced reduction in MS-induced fatigue; 4) ACTH use, although demonstrated to be safe in treating patients with MS, is being used on a twice-weekly basis over a 6 month period, which is a regimen that has not been previously employed, to our knowledge, in MS patients.

C. RESEARCH DESIGN AND METHODS

Study Design

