The proposed study is a 28-week randomized, placebo-controlled, double-blind trial comparing the efficacy of ACTH versus placebo for the treatment of fatigue in patients with RMS (RMS). Ninety patients with RMS who meet all of the eligibility criteria will be enrolled from five participating sites. Eligible patients will be consented by site investigators or delegated research personnel before undergoing any study procedures. Subjects will be randomized to ACTH or placebo at 1:1 ratio.

Endpoints

The primary objective of this study is to assess the efficacy of ACTH versus placebo in reducing fatigability in patients with relapsing MS. The primary endpoint is a statistically significant reduction of fatigue measured by MFIS and FSS, which will be administered at baseline, week 8, 16, 24, and 28.

Secondary objectives include assessment of the tolerability and safety of weekly ACTH treatment vs. placebo and evaluation of ACTH on depression, sleepiness, and quality of life measures and the correlations between measures. The secondary endpoints are measured by BDI-II, ESS, SF-36 at baseline, week 8, 16, 24, and 28. Clinical and laboratory adverse events (AE) and serious adverse events (SAE) will be monitored continuously during the study period to capture safety and tolerability information.

Patient Recruitment

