- Physical and neurological exam
- Laboratory assessments: CBC, Urinalysis, CMP
- MFIS, FSS, BDI-II, ESS, SF36, C-SSR*
- Concomitant therapy and AEs

* The C-SSR must be reviewed by the site principal investigator or treating physician prior to the patient leaving the clinic

Unscheduled visits

Patients may be asked to return for unscheduled visit to assess any undesired clinical, or laboratory changes that occur during the study.

Study withdrawal

If a patient is lost to follow-up after all means of contact have been attempted, she/he will be withdrawn from the study.

Patient Monitoring and Evaluation

Patients will be instructed to contact their treating neurologist immediately in the event of a relapse.

A Stage 1 safety and efficacy analysis will be performed when 45th subject has completed visit 4(week 16). This analysis will be performed by the unblinded clinical and biostatistician members of the data safety monitoring board (DSMB). While this analysis is being performed, no new subjects may enroll in the investigation, but treatment of those already enrolled will continue while the analysis is taking place. If more subjects in the placebo arm demonstrate 20% or greater improvement than in the ACTH arm on both the MFIS and FSS, the study will be halted and subjects in the study will cease receiving investigational agents. If the ACTH arm is equal or superior to the placebo arm in MFIS and/or FSS, the study will continue, as will recruitment of the additional 45 subjects. If the study is halted due to lack of efficacy after the Stage 1 analysis, an additional analysis for efficacy will be performed utilizing those subjects who completed 6 months enrollment at the time the study was halted.

Treatment compliance

Patients will be instructed to complete a medication administration log and return the logs to study coordinator at each visit. Information on missed doses and total number of missed doses will be captured. Missing more than 2 doses in an 8-week interval is considered non-compliant. The investigator will discuss the medication regimen with non-compliant patients and they will be encouraged to continue with their injection schedule.

Potential Pitfalls and Contingencies

This study requires self-administration of an injectable agent. Thus there is a risk of non-compliance on the part of the subjects either due to needle phobia, intolerance to injections or lapse memory on the part of the subjects.

Data Processing and Analysis

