Data forms will be faxed to the data coordination center within 3 business days after each study visit and processed by staff trained in data entry procedures. The forms will be entered by two staff working independently. The completeness of the data and whether the data values are in an appropriate range will be checked periodically. Study sites will be asked to complete data clarification requests for confirmation of missing data or questionable information.

Statistical/Analytical Plan

Primary endpoint

Statistical analysis will be performed to test the change from baseline to end of study in two fatigue measures (MFIS and FSS) to be completed by patient at baseline, Week 8, Week 16, Week 24, and Week 28.

Secondary endpoint

Statistical analysis will be done to test the change from baseline to end of study in depression, sleepiness, and quality of life measures (BDI-II, ESS, and SF-36) to be completed by patient at baseline, Week 8, Week 16, Week 24, and Week 28.

All AEs are to be coded and grouped by organ system. AEs will also be tabulated by severity and by relationship and summarized by treatment group. Summary tables of the AEs will be presented to show the incidence and frequency by treatment group and by study site.

Statistical method

This study will collect longitudinal data that consists of repeated measures on each individual. The mixed-effects regression model for the analysis of longitudinal data will be used to test the changes of the fatigue scores over time.

Sample Size Justification

Ninety subjects will be recruited and randomized 1:1 to receive ACTH or placebo in a subject and examining physician-blinded manner. If the MFIS score decreases from 38 for about 20% with standard deviation =16.4 in the 45 patients who received ACTH, the power to reject the null hypothesis in a paired t-test with alpha=0.5 would be 86%. If the difference of the changes of MFIS score between two treatment group is 7.6 with within group standard deviation=16.4 in the 90 patients, the power to reject the null hypothesis in a t-test with alpha= 0.5 would be 87%. Ziemssen and colleagues (Ziemssen, Hoffman, Apfel, & Kern, 2008) studied the effect of glatiramer acetate on fatigue in MS patients. Glatiramer acetate was found to be associated with a reduction in absence from work and a significant reduction in fatigue symptoms, as measured by MFIS. The data from Ziemssen et al. were used for the sample size calculation for this study.

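### MFIS and FSS are both primary measures, but the plan does not say whether one or both must be significant, and the trial is sized on MFIS alone

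*Combined protocol and SAP*

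**What the plan says.** The Endpoints section in part C reads: "The primary endpoint is a statistically significant reduction of fatigue measured by MFIS and FSS". Under Statistical/Analytical Plan, the Primary endpoint paragraph plans "to test the change from baseline to end of study in two fatigue measures (MFIS and FSS"), and the Statistical method paragraph adds: "The mixed-effects regression model for the analysis of longitudinal data will be used to test the changes of the fatigue scores over time". None of these gives a success rule, a testing order or a division of alpha. The earlier statement in part B, "The primary endpoint of this study is a statistically significant reduction of fatigue in subjects who have RMS", names no scale, so it does not settle the matter.

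Wording about combining the scales appears only under Patient Monitoring and Evaluation, for the Stage 1 analysis. The halt condition begins "If more subjects in the placebo arm demonstrate 20% or greater improvement than in the ACTH arm on both the MFIS and FSS". The continue condition is "If the ACTH arm is equal or superior to the placebo arm in MFIS and/or FSS, the study will continue". Both steer an interim decision. Neither defines success at the end of the trial.

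Sample Size Justification works on MFIS throughout: a fall of about 20% from 38, and then "If the difference of the changes of MFIS score between two treatment group is 7.6", with a standard deviation of 16.4. No effect size, standard deviation or power is given for FSS. Its only number in the document is the entry threshold of 36. Patient Recruitment sets a two-sided alpha of 0.05, power of 0.80 and 20% dropout.

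**The concern.** With two primary scales and no rule, the same data can support opposite conclusions. If MFIS is significant and FSS is not, or the reverse, the plan does not say whether the trial succeeded, and somebody has to decide with the result in view.

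Each way of filling the gap also disturbs a property that the plan states. If both scales are required, the false-positive rate is controlled, but the quoted power describes a single-scale test and is not the trial's power. If either scale is enough at 0.05, power rises, but the two-sided 5% error rate no longer holds.

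**Working it through.** **Inputs from the documents.** Difference 7.6 (20% of 38), SD 16.4, 90 patients randomized 1:1 (45 per arm), from Sample Size Justification. Two-sided alpha 0.05, from Patient Recruitment.

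**Assumptions, because the documents give no figure.** FSS has the same standardized effect as MFIS. The two test statistics are bivariate normal with correlation r from 0 to 0.9.

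**Step 1: the plan's own power figures.**
- Paired t-test, n = 45: noncentrality (7.6/16.4) × √45 = 3.109, power 86.0% at two-sided 0.05. This matches the stated 86%, so the alpha printed there as 0.5 is treated as a misprint for 0.05.
- Two-sample t-test, 45 per arm: noncentrality 7.6 / (16.4 × √(2/45)) = 2.198, power 58.5%. The stated figure is 87%, which appears with 90 per arm (noncentrality 3.109, power 87.1%). That mismatch is a separate issue, so both starting points are carried forward.

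**Step 2: both scales required.** With per-scale power P, joint power = Φ₂(z_P, z_P; r), where z_P is the standard normal quantile of P and Φ₂ is the bivariate normal distribution function. At r = 0 this is P²: 0.87² = 0.757 and 0.585² = 0.342.

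**Step 3: split result.** The probability that exactly one scale is significant is 2 × (P − joint power). At r = 0 and 45 per arm: 2 × (0.585 − 0.342) = 0.486.

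**Step 4: either scale suffices at two-sided 0.05 each, no true effect.** Family-wise error = P(|Z₁| > 1.96 or |Z₂| > 1.96). At r = 0 this is 1 − 0.95² = 9.75%. For a false claim of benefit, only the favourable tail counts: at r = 0, 1 − 0.975² = 4.94%, against 2.5% for one scale.

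| r | Joint power from 87% | Joint power from 58.5% | Split result (from 58.5%) | Family-wise error, either suffices | False claim of benefit |
|---|---|---|---|---|---|
| 0 | 75.7% | 34.2% | 48.6% | 9.75% | 4.94% |
| 0.5 | 78.7% | 42.2% | 32.5% | 9.07% | 4.54% |
| 0.7 | 80.5% | 46.1% | 24.7% | 8.35% | 4.17% |
| 0.9 | 83.2% | 51.5% | 14.0% | 7.04% | 3.52% |

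Simulated t-tests at 45 per arm agree: joint power 0.341 to 0.514, split 0.487 to 0.141.

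**Step 5: sensitivity.** If the FSS effect is half the MFIS effect, joint power at 45 per arm is 11% to 19%. With equal effects and 20% dropout (36 per arm), per-scale power is 49% and joint power 24% to 42%.

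**The case against.** The best reply is that naming MFIS and FSS together already means both. That is the closest reading of the text, and under it there is no inflation of error. But the wording lists instruments and states no decision rule. The same section lists BDI-II, ESS and SF-36 for the secondary endpoints in a similar way, without implying that all must be significant. Even if both was intended, the power for that rule is missing.

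Three stronger readings are tempting and are not supported:

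- **That the plan lets either scale carry the trial.** No final-analysis text says so. The and/or wording belongs to the Stage 1 continue rule only, so the error figures are conditional on a reading that the plan leaves open but does not state.
- **That the missing rule cuts power from 87% to 34%-51%.** Most of that fall, from 87% to 58.5%, comes from the sample-size mismatch. With equal effects and r from 0.5 to 0.9, the both-scales rule itself costs about 8 to 4 points from 87%, or 16 to 7 points from 58.5%.
- **That a split result is the likely outcome.** The 49% figure needs r = 0 between two fatigue scales completed by the same patients at the same visits. At r of 0.5 or more it is 33% to 14%. It reaches 55% to 39% over the full range of r if the FSS effect is half the MFIS effect, but the documents give no basis for that value. Possible is supported; likely is not.

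It is also fair to object to prescribing MFIS as the single primary. The text gives the scales equal standing, so the choice belongs to the sponsor.

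**Conclusion.** The point holds and should be corrected. The plan has two primary scales, no final success rule, and sizing on one of them. The absence of a rule is certain from the text; the numbers are conditional.

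Under the reading closest to the text, error is controlled and the cost is uncomputed power: 76%-83% instead of the stated 87%, or 34%-51% instead of the 58.5% that 45 per arm gives. If either scale were accepted at 0.05, family-wise error would be 9.8% to 7.0% and the chance of a false claim of benefit 4.9% to 3.5%. In a split result, success would be left to a decision made after the data are seen.

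These figures assume an FSS effect equal to that of MFIS, r from 0 to 0.9, a two-sample t-test and no dropout. The planned mixed-effects model was not simulated.

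**What to change.** Before final unblinding, amend the Endpoints section and the Statistical/Analytical Plan to state one error-controlling success rule, and restate the power for that rule. State that the two-scale wording for Stage 1 is interim only. The rule should be set by people who have not seen unblinded Stage 1 results; the plan says of that analysis: "This analysis will be performed by the unblinded clinical and biostatistician members of the data safety monitoring board (DSMB"). The sponsor may choose among:

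1. **MFIS as single primary** at two-sided 0.05, with FSS tested next at 0.05 only if MFIS is significant. Power for the primary claim is that of MFIS (58.5% at 45 per arm). FSS alone can then no longer carry the primary claim. Patients may also enter on FSS alone with MFIS below 38, and for the same percentage change they would show a smaller absolute MFIS fall. The documents do not allow the size of that dilution to be estimated.
2. **Both scales required** at 0.05 each, with joint power stated. This is closest to the current text and keeps the scales equal, at the lower power shown above.
3. **Either scale, alpha split** at 0.025 each. This also keeps the scales equal, but each faces a stricter threshold. At 45 per arm with equal effects, power is 72% to 54% for r = 0 to 0.9, above the 58.5% for MFIS alone until r is about 0.76. If the FSS effect is half the MFIS effect, it is 54% to 47%, a loss at every r.

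No new data or visits are needed. The cost is a short amendment, which Regulatory Requirements says must be approved by the Providence IRB and each site's IRB/IEC.

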1. Patient has a relapse during the study. A relapse is defined as a new symptom, or worsening of pre-existing neurologic symptoms, of at least 24 hours duration, in patients who had been clinically stable for the prior 30 days, in the absence of fever, sleep deprivation or severe emotional stress.
2. Patient has an adverse event that presents unacceptable risk judged by the investigator
3. Patient has inadequate adherence to the protocol
4. Patient is lost to follow-up
5. Patient becomes pregnant

Treatment Overview**Dosage and Administration of Acthar® or matching placebo**

The study drug (ACTH 40 units or identical-appearing placebo) will be given subcutaneously twice weekly for 2 weeks. If the patient tolerates this dosage regimen, the dose will be increased to 80 units or placebo twice weekly. If the 80 unit dosage is not tolerated, the dosage will be reduced to 40 units twice weekly for the remainder of the 24 week participation. The weekly doses will be given 3 days apart, for example, on every Monday and Thursday or every Tuesday and Friday. Patients are not allowed to take doses on consecutive days. If a patient cannot take a dose on a scheduled day, the dose can be taken either a day early, or a day late. Patients that forget to take their scheduled dose will be encouraged to take their dose the following day.

Randomization/Treatment assignment and blinding

A total of 90 patients will be randomized either to active drug (ACTH), or placebo in a 1:1 ratio stratified by study site. Each study site will be assigned a site number, and each patient who signed consent form and received a screening test will have a unique study ID, which identifies the patient and the study site at which they participate throughout the study. Within each site, subjects will be randomized in blocks of 4, 2 ACTH and 2 placebo treated patients, to achieve balance in the allocation of subjects to study drug versus placebo arms. The order in which each of the 4 samples is selected will be predetermined by a

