computer generated randomization schedule. Medications will be labeled and distributed by the coordinating site. The study drugs and matching placebo will be packaged in the same way using identical appearing vials. A unique random number will be printed on the label for each package. A master list containing drug kit numbers and drug assignment (ACTH or placebo) will be kept in a password-protected computer file in the coordinating site pharmacy. Each study site will be required to assign patients in the order of the randomization schedule and dispense medications according to the medication kit numbers indicated on the predetermined randomization schedule. The investigators, study coordinators/nurses, and subjects will remain blinded to randomization assignment until study completion, and the blind will only be violated if, in the judgment of the treating physician, unblinding is necessary for patient safety in the setting of a serious adverse event. The DSMB will not be blinded.

Drug Administration and Storage Instructions

The study drug is supplied in a 5 mL multi-dose vial containing 80 USP units per ml.

Patients will be instructed to inject 40 units subcutaneously twice a week for the first two weeks and 80 units twice a week thereafter, with 3 days between the two doses. Three vials of ACTH will be dispensed at baseline, and 4 vials will be dispensed at Week 8 and Week 16. Each subject is to return used and unused vials, along with their injection log, at each follow-up visit, before they receive their next allotment of drug. Investigational drug use will be recorded in the accountability log by the study coordinator/nurse at each site, and the unused vials will be retained until they are returned to the central coordinating center.

Laboratory Testing and Study Procedure

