
Visit 1 or Screening visit (Week -4 to -1; 7 to 28 days prior to Baseline)

The following clinical and laboratory evaluations will occur within 4 weeks prior to baseline. The investigator/treating neurologist (or designee where allowed) must perform all screening evaluations to determine patient eligibility.

- Informed consent
- Demographics
- Review of medical and neurological history
- Review of medications
- Vital signs
- Physical and neurological exam
- EDSS
- ECG
- Laboratory assessments: Urinalysis, CBC, CMP, TSH, Pregnancy test/HCG (female only)
- MFIS, FSS, BDI-II, ESS, SF36, C-SSR*

* The C-SSR must be reviewed by the site principal investigator or treating physician prior to the patient leaving the clinic

Visit 2 or Baseline visit (Week 0; 4 weeks after Screening +/- 4 days)

The following clinical and laboratory evaluations will occur at baseline visit, which must be completed 4 weeks after screening (+/- 4 days). The investigator/treating neurologist will review inclusion/exclusion criteria to confirm patient eligibility before study drug is dispensed.

- Randomization
- Interval medical and neurological history
- Vital signs
- Physical and neurological exam
- Laboratory assessments: CBC Urinalysis, CMP, Pregnancy test/HCG (female only)
- MFIS, FSS, BDI-II, ESS, SF36, C-SSR*
- Study drug dispensing
- Protocol compliance study drug accountability
- Concomitant therapy and AEs
- Additional serum sample for research purposes

* The C-SSR must be reviewed by the site principal investigator or treating physician prior to the patient leaving the clinic

Visit 3/Week 8 (8 weeks +/- 4 days from baseline)

The following clinical and laboratory evaluations will occur 8 weeks after baseline with a +/- 4 day window. The investigator/treating neurologist will review inclusion/exclusion criteria to confirm patient eligibility before study drug is dispensed.

- Interval medical and neurological history
- Vital signs
- Physical and neurological exam
- Laboratory assessments: CBC, Urinalysis, CMP, Pregnancy test/HCG (female only)
- MFIS, FSS, BDI-II, ESS, SF36, C-SSR*
- Study drug dispensing
- Protocol compliance study drug accountability
- Concomitant therapy and AEs
- Additional serum sample for research purposes

* The C-SSR must be reviewed by the site principal investigator or treating physician prior to the patient leaving the clinic

Visit 4/Week 16 (16 weeks +/- 4 days from baseline)

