An adverse event (AE) is any unfavorable or unintended sign, symptom, or disease that is experienced by a subject who has received an investigational drug, whether or not there is a causal relationship with the investigational drug. At the signing of the informed consent form, each subject will be given the names and telephone numbers of investigational site personnel for reporting adverse events and medical emergencies. The investigator must conduct thorough assessment to determine the severity of the AE and the relationship to the study drug. Any clinically significant AE of severity moderate or higher, requires follow up until resolution or stabilization.

Serious Adverse Events

A serious adverse event (SAE) is defined as any event that:

- Results in the outcome of death
- Places the subject at immediate risk of death (a life-threatening event)
- Results in a congenital anomaly/birth defect
- Results in hospitalization or prolongs an existing hospitalization
- An event that results in persistent or significant disability/incapacity.
- Require intervention to prevent permanent impairment or one of the other outcomes listed in the definition above.

Adverse Event Recording/Reporting

All adverse events (including pre-dosing and treatment-emergent) should be recorded in the subject's Adverse Event CRF regardless of severity or relationship to study drug. The investigator must review the laboratory findings and sign and date the laboratory report. Any moderate or severe laboratory abnormalities should be reported to the coordinating center as outlined below. All SAEs must be reported by the investigator to Providence Regional Research/ Regulatory office by email at [contact] or fax to [contact] within 24 hours of the investigator's knowledge of the event. Providence Health & Services will report SAEs to the FDA. All SAEs must be recorded on SAE forms and be reported, whether or not the event is considered by the investigator to be related to study drug.

Severity

The intensity of severity of an AE will be graded as follows:

Mild	Symptoms(s) barely noticeable to subject or does not make subject uncomfortable; does not influence performance or functioning; prescription drug not ordinarily needed for relief of symptoms(s) but may be given because of personality of subject

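### The patient dosing instruction drops the tolerability condition for the step from 40 to 80 units and omits the step-down, and no contact is scheduled before Week 8 to apply either rule

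*Combined protocol and SAP*

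**What the plan says.** Two parts of section C describe the same step.

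- **Dosage and Administration** sets the rule. After two weeks at 40 units twice weekly, "If the patient tolerates this dosage regimen, the dose will be increased to 80 units or placebo twice weekly". A patient who does not tolerate 80 units goes back to 40 for the rest of treatment.
- **Drug Administration and Storage Instructions** states what patients are told: "Patients will be instructed to inject 40 units subcutaneously twice a week for the first two weeks and 80 units twice a week thereafter". Neither the condition nor the step-down appears there.

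On supply, "Three vials of ACTH will be dispensed at baseline, and 4 vials will be dispensed at Week 8 and Week 16". Each vial holds 5 mL at 80 units per mL.

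On contact, the study flowchart and visit lists go from baseline straight to Visit 3: "The following clinical and laboratory evaluations will occur 8 weeks after baseline with a +/- 4 day window".

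The plan has general safety provisions between visits. Adverse events "will be monitored continuously during the study period to capture safety and tolerability information" (Endpoints). At consent, "each subject will be given the names and telephone numbers of investigational site personnel for reporting adverse events and medical emergencies" (section D, Adverse Event). Under Unscheduled visits, "Patients may be asked to return for unscheduled visit to assess any undesired clinical, or laboratory changes that occur during the study". One discontinuation criterion reads "Patient has an adverse event that presents unacceptable risk judged by the investigator".

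**The concern.** Study drug is self-administered, so the instruction given to the patient decides what is injected. If that instruction omits the condition, a patient with problems at 40 units doubles the dose by following it, contrary to the dosing rule. The dosing rule does not say who judges tolerability or when, and no contact is scheduled around the step at which anyone would ask.

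What is at stake is patient safety. The Background section describes the dose as well tolerated in treating relapses. It also says that the authors know of no earlier use of a twice-weekly regimen over six months in MS, and it makes safety and tolerability of that regimen the fourth secondary endpoint.

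**Working it through.** **1. The two texts side by side**

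| Element | Dosage and Administration | Drug Administration and Storage Instructions |
|---|---|---|
| Start | 40 units twice weekly, 2 weeks | Same |
| Increase to 80 | Only if 40 is tolerated | After two weeks, no condition |
| 80 not tolerated | Back to 40 | Not mentioned |
| 40 not tolerated | No increase, by implication; stopping falls under the adverse-event discontinuation criterion | Not mentioned |

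**2. Does dispensing hold back the increase?** Vials needed = total units / 80 units per mL / 5 mL, rounded up.

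- Weeks 0 to 8, escalated: 2 × 2 × 40 + 6 × 2 × 80 = 160 + 960 = 1,120 units = 14 mL, so 3 vials. This reproduces the plan's baseline figure.
- Weeks 8 to 16 at 80 units: 8 × 2 × 80 = 1,280 units = 16 mL, so 4 vials. This reproduces the plan's later figure.
- Weeks 0 to 8, held at 40: 8 × 2 × 40 = 640 units = 8 mL, so 2 vials.

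The baseline supply is 3 × 5 mL × 80 = 1,200 units, which covers the 1,120 units of full escalation. The patient therefore already holds the drug for 80 units, and supply does not hold back the step.

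**3. Exposure before the first scheduled contact**

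- Nominal: 6 weeks × 2 = 12 injections of 80 units, which is 960 of the 1,120 units due by Week 8 (86%).
- For a patient who should have stayed at 40, the most this could add is 12 × (80 − 40) = 480 units.
- With the visit window, assuming a first injection on Day 0 and doses on Days 0, 3, 7, 10, 14, 17 and so on: 11 injections of 80 units fall before Day 52 and 12 before Day 56. Before Day 60 the supply caps the number at 13, because 15 mL less 2 mL for the four 40-unit doses leaves 13 mL. The range is 11 to 13.

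The Day 0 start is an assumption. The plan does not say that the first injection is given at the baseline visit, and it lets a dose be taken one day early or late. The 12 is therefore nominal, and a check tied to a fixed study day could fall on the wrong side of the step.

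**4. How many patients?** The documents give no rate of intolerance at 40 units, no rate of non-reporting and no dose-response. Neither a count of affected patients nor an effect on MFIS or FSS can be derived.

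**The case against.** The strongest reply is that the second text is shorthand. It sits beside vial sizes and counts and describes the nominal regimen, while the dosing rule governs. It leaves out the step-down as well, and nobody would take that as cancelling the step-down. Handing out three vials does not show that the condition was abandoned, since a site must supply the highest permitted dose. Between visits there are telephone numbers, continuous adverse-event monitoring and unscheduled visits, and the step-down rule itself presumes that patient and site can talk between visits.

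Much of this stands. The shorthand reading is possible, and the vial count shows only that supply does not block the step. It does not remove the conflict. The sentence says what patients will be told, no other text gives the patient the condition, and none of the general provisions is tied to the step. In practice they depend on the patient raising a problem, and the instruction as written gives no prompt to do so before doubling the dose.

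Three stronger readings are not supported:

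- *Every patient will in fact receive an unconditional instruction.* The patient sheet and injection log are not among the documents, so only the protocol's statement of the instruction can be judged.
- *A known number of excess injections will follow.* That needs a patient who does not tolerate 40 units, tells nobody, doubles the dose and continues for six weeks, at a rate nowhere given.
- *The plan has no safety oversight before Week 8.* It has oversight, but none of it is scheduled around the increase.

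**Conclusion.** The concern holds as a conflict between two stated rules. The increase is conditional and reversible in the dosing rule, but unconditional and without a step-down in the patient instruction. Neither dispensing nor a scheduled contact closes the gap before Week 8, by which time about 12 injections of 80 units would nominally have been taken.

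That figure rests on the plan's twice-weekly schedule and a step at two weeks. It describes what following the instruction entails and does not predict harm. How many patients would be affected is unknown.

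A reader might infer that the fatigue comparison is biased or loses power. The documents give no basis for that, and it is not claimed. A reader might also infer that dose-level information is lost. It is not: used and unused vials are returned at each visit, and a patient held at 40 would open 2 + 2 + 2 vials against 3 + 4 + 4 at full dose, if each vial is used until empty.

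Severity is minor to moderate, on patient-safety grounds only.

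**What to change.** **Reword the patient instruction to match the dosing rule.** For example:

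> Inject 40 units twice a week for two weeks (four injections). Go up to 80 units twice a week only if you have tolerated 40 units. If you have a troublesome adverse event at 40 units, do not go up, and call the site before your next injection. The investigator will decide whether you stay at 40, go up or stop study drug. If you do not tolerate 80 units, call the site; you will return to 40 units twice a week for the rest of treatment.

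The decision to stop stays under the existing adverse-event discontinuation criterion. This wording does not keep an intolerant patient on 40 units by default. It also restores the step-down, which protects patients already taking 80 units.

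**Preferably, add one telephone call.** The blinded coordinator makes it, with the same script in both arms, after the fourth 40-unit injection and before the first 80-unit injection. Time it by injection and not by study day, given the flexible dosing days. If the call is adopted, the patient wording must also say that the dose stays at 40 units until the site has confirmed the increase, so that a missed call cannot lead to an unchecked step.

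**Cost.** The rewording is a few sentences. The call means about 90 short conversations plus repeat attempts, and an occasional short delay. The nominal course is 4 × 40 + 44 × 80 = 3,680 units, so each injection held at 40 forgoes 40 / 3,680 = 1.1%. The call may raise adverse-event reporting somewhat in both arms. It does not replace blood pressure or laboratory checks, which would still first occur at Week 8.

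Recording the dose level of each injection in the existing log is optional. It would make tolerability easier to report, but the point does not depend on it.
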